17.4. Blinding Analysis

A Statistical Analysis Plan (SAP) will be finalized prior to breaking the blind, which will include a plan for blinding analysis. The extent to which subjects remained blinded at the end of Phase 1 will be assessed by calculating a blinding index based on data from the Blinding Assessment following Phase 1, in which subjects will be asked what treatment they believe they received. Further, participants who guess that they received "Treatment" or "Sham" (as opposed to "Don't Know") will be asked for the primary reason for their guess and these results will be analyzed.

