A blinding assessment will be conducted following Phase 1, in which participants will be asked what treatment they believe they received. The study participants will state their belief regarding their treatment group assignment (i.e., "Treatment", "Sham", or "Don't Know"). A logistic regression analysis will be conducted using data collected at the blinding assessment to assess the blinding. The dependent variable for this analysis will be the participant's guessed treatment, and the explanatory variables will be the participant's actual treatment and the following two PGI-I Day 28 indicator variables: (1) being at least "minimally improved" and (2) being at least "much improved". The PGI-I variables will be used as measures of treatment efficacy. Cases for which the guessed treatment is "Don't Know" or missing will be excluded from the analysis. The estimated coefficient for the actual treatment will be presented, together with the p-value for testing the null hypothesis that the coefficient equals 0 versus the alternative hypothesis that the coefficient does not equal 0. This analysis will be based on the ITT Population. The purpose of the blinding analysis is to evaluate whether there is statistical evidence that the study blinding was compromised. The approach to be taken is to examine whether the actual treatment is predictive of the participant's guessed treatment, after taking into account treatment efficacy.

Further, participants who guess "Treatment" or "Sham" (as opposed to "Don't Know") will be asked for the primary reason for their guess and the results will be summarized by treatment group using frequencies and percentages.

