Preferred Term 2	(x:x) xx	(x.xx) xx	xx (xx.x)	xx (xx.x)	xx (xx.x)	xxx (100.0)	×

Creation date, time Program Name: Source: Listing 4

[Programmer's Note: This table will be continued for Sham (Between Randomization and Day 28) and NTX100 (Between Day 28 and Day 56).]

Noctrix Health Inc. Protocol Number: CT-04

Table 3.6

ADVERSE EVENTS (AES): INCIDENCE BY ANTICIPATED OBSERVATION (AO) CODE, AND BY TREATMENT AND TIME PERIOD (EVENT LEVEL)

SAFETY ANALYSIS POPULATION		Sham	(xx=N)	(%) u	(x.x)	xx (xx.x)	xx (xx.x)	xx (xx.x)	(x.xx) xx
SAFETY		NTX100	(xx=N)	(%) u	(x.xx) xx	(xxx)	(xxx)	(xxx) xx	(x.x.x) xx
	Between Randomization and Day 28			AO Code	AO Code 1	AO Code 2	AO Code 3	AO Code 4	AO Code 5

Program Name: Source: Listing 4 Note: Percentages are based on N, the total number of AEs with a non-missing AO code.

Creation date, time

[Programmer's Note: This table will be continued for NTX100 (Between Day 28 and Day 56).]

Table 4

Page x of y

BLINDING ANALYSIS ITT POPULATION

		NTX100	Sham
Variable	Statistic	(N=xx)	(N=xx)
Which device do you think you received for the past 4 weeks? (#1)			
Treatment	u (%) u	xx (xx.x)	xx (xx.x)
Sham	u (%) u	xx (xx.x)	xx (xx.x)
Don't Know	u (%) u	xx (xx.x)	xx (xx.x)
If 'Treatment' or 'Sham' in #1, what was the primary reason for this guess?			
Relief of RLS symptoms	n (%)	xx (xx.x)	xx (xx.x)
Side-effects	u (%) u	xx (xx.x)	xx (xx.x)
Other	n (%)	xx (xx.x)	xx (xx.x)
If 'Treatment' or 'Sham' in #1, Participant's guessed treatment (1)	Coefficient for Actual Treatment	x.x	
	p-value	X.XXXX	

Creation date, time		jistic regression analysis. The dependent variable was the participant's guessed treatment, and the explanatory variables were the participant's actual treatment and the following two PGI-I Day 28	at least 'improved' and (2) being at least 'much improved'. The p-value is from a two-sided test of the null hypothesis that the true coefficient for the actual treatment equals 0 versus the alternative	int does not equal 0.
Program Name:	Source: Listing 5	(1) Results are based on a logistic regression analysis. The dependent var	indicator variables: (1) being at least 'improved' and (2) being at least '	hypothesis that true coefficient does not equal 0.

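### The only formal blinding test drops Don't Know answers, so it cannot detect an arm difference in certainty when guessers in both arms split alike

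*SAP*

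**What the plan says.** Protocol 17.4 announces how blinding will be judged: "The extent to which subjects remained blinded at the end of Phase 1 will be assessed", specifically "assessed by calculating a blinding index based on data from the Blinding Assessment following Phase 1". It does not name the index, and it leaves the detailed plan to the SAP.

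SAP 9.0 records three possible answers and specifies a logistic regression of guessed treatment on actual treatment plus two PGI-I Day 28 indicators (at least minimally improved, at least much improved). On the indicators it says "The PGI-I variables will be used as measures of treatment efficacy"; SAP 5.2 lists the same covariates. On who enters the model it says "Cases for which the guessed treatment is 'Don't Know' or missing will be excluded from the analysis". The analysis is said to be based on the ITT Population. Its aim is explicit: "The purpose of the blinding analysis is to evaluate whether there is statistical evidence that the study blinding was compromised".

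The Table 4 shell prints counts and percentages of Treatment, Sham and Don't Know by arm under the question "Which device do you think you received for the past 4 weeks? (#1", then the main reason for the guess, then one coefficient and one p-value. Its footnote reads "The p-value is from a two-sided test of the null hypothesis that the true coefficient for the actual treatment equals 0". No significance level is given for this test: SAP 5.1 sets levels for efficacy and safety only.

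The SAP defines no blinding index, and SAP 3.5, which lists changes from the protocol's analyses, does not mention its absence.

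**The concern.** Don't Know is a valid answer given after treatment, and the arm can influence it. Someone who can tell what they received tends to commit; someone who cannot tends not to. The setting makes an arm difference plausible. Both modes share a noticeable ramp of about 30 seconds (Protocol 5, SAP 3.3), so sham subjects feel something and may stay unsure, while active mode is designed to produce continuing muscle activation (Protocol 1.5).

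Restricting the model to guessers removes this part of the evidence from the only inferential statement about the blind. The efficacy endpoints are reported by the subject or, for CGI-I, rated by the investigator after seeing the subject's PGI-I (Protocol 16.14). A non-significant p-value would be the main formal support for the blind, and it could stand beside a large imbalance in certainty that no planned statistic addresses.

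**Working it through.** **Arm sizes.** Protocol 17.2 plans 112 completers and 15% dropout: 112/0.85 = 131.8, rounded up to 132, which reproduces the plan. That gives 66 per arm randomized and 56 per arm completing. The documents give no expected answer rates, so all rates below are assumptions. A two-sided 0.05 level is also assumed. Answers are always in the order Treatment / Don't Know / Sham.

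**Why the coefficient cannot move.** Among guessers, the log-odds of saying Treatment is log(pT/pS); pDK does not appear. The arm coefficient is log[(pT/pS) on active ÷ (pT/pS) on sham]. In a model of all three answers, let bT and bS be the arm effects on log(pT/pDK) and log(pS/pDK). The planned coefficient is then bT − bS. A pure certainty difference has bT = bS, not zero, so the planned coefficient is zero. The same cancellation holds within each PGI-I level.

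**Worked table, 56 per arm.** Active 40/6/10, sham 16/36/4.

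- Guessers' odds ratio: (40 × 4)/(10 × 16) = 1.00; Fisher p = 1.0.
- Treatment answers: 40/56 = 71% against 16/56 = 29%.
- Don't Know: 6/56 = 11% against 36/56 = 64%; Fisher p = 4.6 × 10⁻⁹.
- All three answers: column totals 56, 42 and 14 give expected counts 28, 21 and 7 per arm. Chi-square = 2 × (12²/28 + 15²/21 + 3²/7) = 34.3 on 2 df, p = 3.6 × 10⁻⁸.
- A per-arm index (correct minus incorrect guesses, over all answers): active (40 − 10)/56 = +0.54; sham (4 − 16)/56 = −0.21.

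**Planned model with both PGI-I terms, 2,000 trials per scenario.** In the first three rows 80% of guessers in each arm say Treatment.

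| Share guessing, active vs sham | Guessers saying Treatment | Planned test, 56 (66) per arm | Unadjusted 3×2 test, 56 (66) per arm |
|---|---|---|---|
| 90% vs 40% | 80% both | 3.4% (4.5%) | 100% (100%) |
| 80% vs 50% | 80% both | 3.8% (4.0%) | 86% (92%) |
| 90% vs 20% | 80% both | 2.9% (3.0%) | 100% (100%) |
| 90% vs 40% | 90% vs 50% | 90% (96%) | – |
| 90% vs 20% | 90% vs 50% | 71% (81%) | – |
| 90% vs 20% | 85% vs 60% | 42% (48%) | – |

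The last three rows show that the planned test works when guessers' answers also differ, with power falling as fewer sham subjects guess.

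**Which three-level analysis, 66 per arm, no covariates.** The ordered test ranks Sham < Don't Know < Treatment.

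| Active vs sham | Guessers only | Ordered test |
|---|---|---|
| 60/30/10 vs 30/65/5 | about 3% | 79% |
| 54/37/9 vs 36/58/6 | about 3% | 39% |
| 35/50/15 vs 15/50/35 | 92% | 92% |
| 25/70/5 vs 35/30/35 | 72% | 31% |
| 45/10/45 vs 15/70/15 | – | 7–10% |
| No difference | 4–5% | 4–5% |

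The ordered test misses symmetric certainty differences and can lose power when Don't Know differs by arm. For 45/10/45 vs 20/60/20 it rejects in 7%, an unordered 3×2 test in about 100%. The unordered test costs a little when Don't Know is balanced: about 86% against 92% in the third row.

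**Why the PGI-I terms must stay.** Simulate an intact blind in which guesses depend only on PGI-I, with 45% vs 15% much improved. A three-level (ordinal) model with treatment alone calls the blind broken in about 47% of trials. With the PGI-I terms the figure is 5–6%. In a separate assumed certainty-only scenario, analysing all three answers with the PGI-I terms kept detected the difference in 65% of trials, against 3% for the planned model.

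**The case against.** A reader might infer that an imbalance in certainty would be hidden and a compromised blind reported as intact. The documents do not support that. Table 4 prints Don't Know by arm in the same table as the p-value, with the reasons for guessing, and Listing 5 shows each answer. The SAP has no rule that a non-significant result means an intact blind; it asks only whether there is evidence of compromise. This stands. What remains is that the imbalance is shown without a test, an interval or a rule for reading it.

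The failure also needs a particular pattern: the same Treatment-to-Sham ratio among guessers in both arms. No document figure says this will occur, and away from it the planned test had 42% to 96% power in the cases tried. This stands too, and it is why the planned model should be kept.

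A further objection is that subjects may commit because they feel better rather than because they recognize the stimulation. A certainty difference is therefore not proof of unblinding. This is correct, and it argues for keeping the PGI-I adjustment, not for leaving Don't Know out.

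Finally, the blinding analysis is supportive. It gates no endpoint in SAP 5.6 and does not enter the primary test in SAP 8.1. That limits the weight of the point without removing it.

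**Conclusion.** The point holds in a limited form. The only formal blinding test conditions on having guessed. When guessers split alike in both arms it rejects at or below its nominal level however large the difference in Don't Know: 2.9% to 4.5% in the adjusted simulations, where an unadjusted three-category test rejects in 86% to 100%. Nothing else planned fills the gap, because Table 4 is descriptive and the protocol's index was dropped without being listed as a change.

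The algebra needs no assumed rates; the percentages do, and they rest also on 56 or 66 answers per arm and a two-sided 0.05 level. The finding does not say that the blind will fail, that an imbalance would go unreported, or that an imbalance would prove unblinding. Nor is every analysis that retains Don't Know better: an ordered one can do worse than the planned test.

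**What to change.** In SAP 9.0 and Table 4, add a formal analysis of the three-level answer (Treatment / Don't Know / Sham) in every ITT subject who answered, excluding only missing answers. Use a multinomial (generalized-logit) model with actual treatment and the two PGI-I Day 28 indicators, and test treatment jointly on 2 df. Keep the planned guessers-only logistic model beside it. State the significance level and how the two results will be read together, including that a certainty difference is a signal and not proof. In SAP 3.5, record what replaces the protocol's blinding index, or define the index in SAP 9.0. SAP 5.2 needs a matching line, since it names the logistic regression as the only covariate-adjusted blinding analysis.

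The cost is SAP wording, one model statement and a line or two in Table 4, with no new data. The statistical price is one extra degree of freedom: slightly lower power than the guessers-only test when Don't Know is balanced (about 86% against 92%, unadjusted 3×2 test).

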### **5.2** Adjustments for Covariates

There will be no adjustment for covariates in any efficacy or safety analysis, unless there are missing data for the primary efficacy endpoint and multiple imputation methods are used (see Section 5.3). Only the logistic regression analysis conducted to assess the blinding will include adjustment for covariates. The dependent variable for this analysis will be the participant's guessed treatment, and the explanatory variables will be the participant's actual treatment and the following two PGI-I Day 28 indicator variables as covariates: (1) being at least "minimally improved" and (2) being at least "much improved".

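### The only inferential check on the blind is adjusted for same-visit PGI-I, so it cannot show by itself whether the blind was compromised; an unadjusted measure should stand beside it

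*SAP*

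**What the plan says.** SAP 9.0 gives the aim: "The purpose of the blinding analysis is to evaluate whether there is statistical evidence that the study blinding was compromised". It then states how: "The approach to be taken is to examine whether the actual treatment is predictive of the participant's guessed treatment, after taking into account treatment efficacy". The method is a logistic regression of the participant's guess on actual arm and two Day 28 PGI-I indicators, at least minimally improved and at least much improved. Of these it says: "The PGI-I variables will be used as measures of treatment efficacy". The arm coefficient is reported with a p-value for "testing the null hypothesis that the coefficient equals 0 versus the alternative hypothesis that the coefficient does not equal 0". SAP 5.2 repeats the model, naming "the following two PGI-I Day 28 indicator variables as covariates". On undecided subjects: "Cases for which the guessed treatment is 'Don't Know' or missing will be excluded from the analysis".

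The Table 4 shell also shows the raw guesses (Treatment, Sham, Don't Know) and the primary reason for the guess (relief of RLS symptoms, side-effects, other) as counts and percentages by arm. Its only inferential entries are the adjusted coefficient and its p-value.

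Protocol 17.4 planned something else. The extent of blinding "will be assessed by calculating a blinding index based on data from the Blinding Assessment following Phase 1". No index appears in SAP 5.2, SAP 9.0 or Table 4, and SAP 3.5 does not list its omission as a change.

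**The concern.** The tested null is that guess and arm are independent given the two PGI-I indicators. This matches an intact blind only if the two cut-points capture the relief that subjects feel, and belief about the arm does not move PGI-I. The SAP states neither condition. PGI-I and the blinding question are both answered at Day 28 (EVAL 6 in the schedule of assessments), and both are the subject's own judgement.

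The second condition matters most in this trial. Under Protocol 16.14 the investigator scores CGI-I, the primary endpoint, after reviewing the subject's PGI-I. If subjects recognized their arm and rated accordingly, that expectancy could pass through PGI-I into the primary result. In that situation the adjusted test is weakest, and a non-significant coefficient would be read as reassurance.

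**Working it through.** **The plan's own figure.** The documents give no number for the blinding test. The sample size reproduces: 112 / (1 − 0.15) = 131.8, so 132. The checks use the 112 completers, 56 per arm.

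**Effect sizes implied by the plan (SAP 3.4).** For a two-sample t-test at two-sided 0.05 and 85% power, d ≈ (1.960 + 1.036) × √(2/n per arm).
- IRLS, N = 112: 2.996 × √(2/56) = 0.57.
- CGI-I score, N = 36: 2.996 × √(2/18) = 1.00 (1.03 with the t correction).

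These stand in for the arm difference in felt relief.

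**Assumptions not in the documents.** Two-sided 0.05 for the arm coefficient (SAP 5.1 sets levels only for efficacy and safety tests); 25% Don't Know, dropped as planned; PGI-I cut-points at the 35th and 62nd percentiles of pooled response; 1,500 replicates, so the Monte Carlo standard error near 5% is √(0.05 × 0.95/1500) = 0.6 points.

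**A. Intact blind, working device.** Felt relief is L = N(0,1) + d × arm. PGI-I is L plus N(0, s²) noise, cut at the two points. The guess is the sign of λ(L − d/2) plus logistic noise, so arm reaches the guess only through relief. Within-arm PGI-I reliability is 1/(1 + s²): 1.0, 0.8 and 0.5 for s = 0, 0.5 and 1.

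| d | λ | Planned, s = 0 | Planned, s = 0.5 | Planned, s = 1 | Without PGI-I terms |
|---|---|---|---|---|---|
| 0.57 | 1 | 6.0% | 8.2% | 13.1% | about 27% |
| 0.57 | 2 | 4.8% | 9.7% | 24.1% | 50–51% |
| 1.0 | 1 | 6.8% | 13.6% | 29.5% | 65–66% |
| 1.0 | 2 | 6.5% | 20.7% | 54.5% | 92–94% |

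With d = 0 the planned test rejects 4–6%. With Don't Know at 0% or 40%, the worst cases (λ = 2, s = 1) stay at 23–24% for d = 0.57 and 48–52% for d = 1.0.

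**B. Broken blind, inert device.** A cue moves belief enough to give an unadjusted arm coefficient of about 1.28, and belief then shifts PGI-I.

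| Expectancy shift in PGI-I (SD) | Planned test rejects | Without PGI-I terms | Median adjusted coefficient |
|---|---|---|---|
| 0 | 80% | 81% | 1.32 |
| 0.5 | 77% | 80% | 1.32 |
| 1 | 62% | 79% | 1.24 |
| 2 | 30% | 80% | 1.15 |
| 3 | 9% | 81% | 1.07 |

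The coefficient shrinks only modestly, so much of the loss is precision. A second formulation of the link from belief to PGI-I gave 76%, 70% and 53% at 0.5, 1 and 2 SD, so the form of the link matters. With a stronger leak (unadjusted coefficient about 2.1), power is still 95% at a 1 SD shift.

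**C. Cue acting wholly through expectancy-driven PGI-I.** There is no true effect; reported relief differs by arm and drives the guess. The planned test rejects 4–7%; the model without PGI-I rejects 27–97%. The generating equations are the same as in A with s = 0. Guess and PGI-I data alone therefore cannot distinguish guessing from real relief from guessing from expectancy-driven relief, whichever model is fitted.

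**The case against.** SAP 9.0 states openly that it tests arm after allowing for efficacy, and for good reason: with a working device, subjects guess correctly because they feel better. In every working-device case in A, adjustment lowered the false-flag rate, for example from about 50% to 5–24% at d = 0.57 with λ = 2. This stands. A reader might infer that the model asks the wrong question, or that it will generally report a broken blind when the device works. The documents support neither: the adjustment serves a declared purpose, and false flags are about 5–7% when PGI-I tracks relief well.

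Table 4 already gives raw guesses and reasons by arm, so a reader could compute the unadjusted association. This also stands, and it limits the gap to a missing planned measure and a missing rule for reading the two together.

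A reader might also infer that an unadjusted test would settle the matter. It would not. It rejects often whenever relief differs by arm, whether the blind is broken or intact. That limit belongs to end-of-phase guess data, not to this SAP alone.

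Finally, the analysis sits under Other Analyses, and no efficacy decision or step in the testing sequence depends on it. That is correct and bounds the consequence.

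**Conclusion.** The concern holds in a limited form. The adjusted coefficient is a reasonable supportive analysis but cannot by itself answer the purpose that SAP 9.0 gives it. With an intact blind and a working device it rejected about 5–24% (d = 0.57) or 7–55% (d = 1.0) of the time. With a leak and an inert device, its power fell from 80% to 77% or 76% at a 0.5 SD expectancy shift, and to 30% or 53% at 2 SD, depending on how belief feeds PGI-I.

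PGI-I reliability, the strength of the link from relief to guess, the size of the leak and the size of the expectancy effect are all assumed. The ranges illustrate possible behaviour and do not predict this trial. The direction of both errors follows from conditioning on a coarse self-rating that belief may influence.

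Nothing here shows that the blind is or will be broken, and the primary test is unaffected. What changes is the conclusion allowed about the blind: a non-significant adjusted coefficient is not evidence that it held.

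**What to change.** In SAP 5.2, SAP 9.0 and Table 4:

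1. Keep the planned adjusted model and label it supportive.
2. Add an unadjusted measure of the guess–arm association: either the blinding index by arm promised in Protocol 17.4, counting Don't Know, or the same logistic model without the PGI-I terms. If the index is not restored, record that in SAP 3.5.
3. Reword the purpose. The unadjusted measure shows whether guesses were associated with arm; the adjusted coefficient shows how far reported benefit may account for it. Read both with the reason-for-guess table. Report a significant unadjusted result beside a non-significant adjusted one as 'guess associated with arm; relief and unblinding not separable', not as an intact blind.

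The cost is some SAP wording and one added measure in Table 4, with no new data. The downside is that, with an effective device, the unadjusted association will usually be significant from relief alone, and the report must say so.

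Replacing the two indicators with the 7-level PGI-I plus IRLS reduction is not recommended. It lowers false flags, but IRLS is also rated by the subject at Day 28. In a run with PGI-I reliability 0.8, about 12% Don't Know and a 1.0 SD cue entering both scales, it cut detection from 27% to 7%.

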# Appendix A: TABLE SHELLS

Table 1

DEMOGRAPHICS AND BASELINE CHARACTERISTICS ITT POPULATION

Variable	Statistic	NTX100 (N=xx)	Sham (N=xx)
Age (vears) (1)	c	X	×
	Mean	XX.XX	XX.XX
	Median	xx.xx	xx.xx
	SD	xx.xx	XX.XX
	Minimum - Maximum	XX.X - XX.X	XX.X - XX.X
Sex (at birth)			
Male	n (%)	xx (xx.x)	xx (xx.x)
Female	n (%)	xx (xx.x)	xx (xx.x)
Ethnicity			
Hispanic or Latino	n (%)	xx (xx.x)	xx (xx.x)
Not Hispanic or Latino	l (%) u	xx (xx.x)	xx (xx.x)
Race			
American Inidan or Alaska Native	n (%)	xx (xx.x)	xx (xx.x)
Asian	n (%)	xx (xx.x)	xx (xx.x)
Black or African American	(%) u	(x.xx) xx	xx (xx.x)
Native Hawaiian or Other Pacific Islander	u (%)	xx (xx.x)	xx (xx.x)
White	u (%)	(x.x)	xx (xx.x)
Height (inches)	C	×	×
	Mean	XX.X	XX.X
	Median	xx.x	xx.x
	SD	xx.x	xx.x
	Minimum - Maximum	XX - XX	XX - XX
Weight (lbs)	c	×	×
	Mean	XXX.XX	XXX.XX
	Median	xxx.xx	xxx.xx
	SD	xxx.xx	xxx.xx
	Minimum - Maximum	XXX.X - XXX.X	XXX.X - XXX.X
BMI (kg/m^2)	د	X	XX
	Mean	XX.XX	xx.xx
	Median	XX.XX	xx.xx
	SD	xx.xx	XX.XX
	Minimum - Maximum	XX.X - XX.X	XX.X - XX.X
IRLS Total Score at Baseline	L	××	××
	Mean	XX.X	XX.X

Noctrix Health Inc. Protocol Number: CT-04

	Median	XX.X	XX.X
	SD	XX.X	XX.X
	Minimum - Maximum	XX - XX	XX - XX
Duration of RLS symptoms (years)	Ц	×	×
	Mean	XX.XX	XX.XX
	Median	xx.xx	XX.XX
	SD	xx.xx	XX.XX
	Minimum - Maximum	XX.X - XX.X	XX.X - XX.X
Categories of medication that the subject is refractory to			
Dopamine agonist - Ropinirole, Pramipexole, Rotigotine	n (%)	xx (xx.x)	xx (xx.x)
Alpha-2-delta ligand - Gabapentin, Pregabalin, Gabapentin Enacarbil	n (%)	xx (xx.x)	xx (xx.x)
Both	n (%)	xx (xx.x)	xx (xx.x)
Categories of medication curently taking (2)			
Dopamine agonist	n (%)	xx (xx.x)	xx (xx.x)
Alpha-2-delta ligand	n (%)	xx (xx.x)	xx (xx.x)
Opioid	n (%)	xx (xx.x)	xx (xx.x)
Benzodiazepine	n (%)	xx (xx.x)	xx (xx.x)
Other	n (%)	xx (xx.x)	xx (xx.x)

Program Name:
Source: Listing 1.2, 1.3, and 3
(1) Age = (Visit date - Date of Birth)/365.25.
(2) More than one category may apply, so the percentages may sum to more than 100%.

Creation date, time

Noctrix Health Inc. Protocol Number: CT-04

Table 2.1

